Population	
Key Inclusion Criteria
 
 • Age \geq18 years. • Able and willing to avoid high altitude travel until gas resolution (approximately 6 to 8 weeks). • For phakic patients, able and willing to avoid supine positioning until gas resolution (approximately 6 to 8 weeks). • At least one eye with each of the following:

PARTICIPANT AREA	DESCRIPTION
	
 ○ central vitreomacular adhesion on OCT that is no larger than 3000 microns, confirmed by central reading center, ○ decreased visual function (e.g. metamorphopsia or other visual symptom) that is attributed to VMT, ○ best corrected Early Treatment Diabetic Retinopathy Study (ETDRS) visual acuity equivalent of 20/32 to 20/400, and ○ prompt vitrectomy not required 
Key Exclusion Criteria
 
 • Macular or lamellar hole. • Other condition that might affect visual acuity during the course of the study (e.g. retinal vein occlusion, advanced age-related macular degeneration, or macular edema induced by a condition other than VMT). 
 ○ Note: Epiretinal membrane is not an exclusion nor a requirement. • High level myopia (-8.00 diopters or more negative if phakic; retinal abnormalities consistent with pathologic myopia if phakic or pseudophakic). • Prior gas injection, ocriplasmin injection, or intraocular injection for any reason. • Prior vitrectomy.
Sample Size	Minimum of 124 eyes
Treatment Groups	
Random assignment (1:1) to one of the following:
 
Group A: PVL (0.3-mL C₃F₈ injection)
 
Group B: Observation (Sham injection)

Participant Duration	24 weeks
Protocol Overview/Synopsis	
 1. Informed consent will be obtained for screening. 2. Eligibility will be assessed, including reading center confirmation of VMT on OCT. 3. Eligible eyes will be randomly assigned to C₃F₈ injection (0.3 mL) or sham injection, which will be performed on the day of randomization. 4. Follow-up will occur at 1, 4, 12 and 24 weeks and consist of vision testing (including visual acuity and visual function (myVisionTrack), ocular exam, and OCT). 5. Rescue vitrectomy may be performed if there is a 10 or more letter decrease at one visit or 5 or more letter decrease at two consecutive visits compared

PARTICIPANT AREA	DESCRIPTION

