295 (including protocol refraction) in each eye (*within prior 8 days*)

- 296 4. Visual function testing (myVisionTrack) (*within prior 8 days*)
 - 297 ➤ Visual function testing will be performed using the myVisionTrack application on an
298 iPad or tablet. myVisionTrack® is an FDA cleared application to track disease
299 progression in patients with certain retinal diseases. During the test, the patient will
300 select the circle that is shaped differently among a series of side-by-side circles on the
301 screen. The series continues with increasing difficulty until the patient's visual
302 function is determined. Visual function is measured using the shape discrimination
303 hyperacuity (SDH) (logMAR) score.

- 304 5. Spectral-Domain OCT using Zeiss Cirrus or Heidelberg Spectralis on each eye (*within prior
305 8 days*)

306 ➤ OCT scans of the study eye will be promptly sent to the central reading center for
307 grading and a participant cannot be randomized until reading center confirmation of
308 eligibility has been received

309 6. Ocular examination on each eye including slit lamp, measurement of IOP, lens assessment,
310 and dilated ophthalmoscopy (*within prior 8 days*)
311 ➤ Scleral depression to rule out any retinal tears pre-operatively will be required for the
312 baseline eye exam to confirm eligibility

313 **2.4 Randomization of Eligible Participants**

314 Randomization may occur on the same day as baseline testing if eligibility is confirmed by the
315 reading center on the day of screening.

316 1. Prior to randomization, the participant's understanding of the trial, willingness to accept the
317 assigned treatment group, and commitment to the follow-up schedule should be reconfirmed.
318 2. The baseline injection (or sham) must be given on the day of randomization; therefore, a
319 participant should not be randomized until this is possible.
320 3. Randomization is completed on the DRCR Retina Network website.
321 • Study eyes will be randomly assigned with equal probability to one of two treatment
322 groups:
323 ○ Group A: PVL (Intravitreous injection of 0.3 mL C₃F₈ gas)
324 ○ Group B: Observation (Sham injection)

325 Randomization will be stratified by clinical site and presence of epiretinal membrane (ERM)
326 within 1 mm of the center of the macula, determined by Reading Center grading. Previous
327 reports have suggested that the proportions of eyes with VMT release differ depending on the
328 presence of ERM.

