 - 395 • An extended ophthalmoscopy including a scleral depression is required at 1, 4, and 12
396 weeks to identify any retinal tears or detachments

397 All of the testing procedures do not need to be performed on the same day, provided that they are
398 completed within the time window of a visit. If data from a testing procedure is unusable (e.g., if
399 OCT is ungradable), the participant may be asked to repeat the procedure during an additional
400 visit, whether part of usual care or solely to repeat the procedure.

401 **4.1.2 Unscheduled Visits**

402 Additional visits may occur as required for usual care of the study participant.

403 Testing procedures at unscheduled visits are at investigator discretion. However, it is
404 recommended that procedures that are performed should follow the standard DRCR Retina
405 Network protocol for each procedure.

406 **4.2 Treatment During Follow-Up**

407 **4.2.1 Criteria for Vitrectomy**

408 Vitrectomy may be performed if one of the following occurs:

409 1. Visual acuity decreases at least 10 letters at a single visit (not including the 1-week visit) or
410 at least 5 letters at two consecutive visits (not including the 1-week visit) compared with
411 baseline that is thought to be related to VMT

412 2. Complication requires prompt surgical intervention (e.g., macular hole, retinal detachment,
413 non-clearing vitreous hemorrhage)

414 Otherwise, protocol chair approval must be obtained for alternative treatment.

415 **4.2.2 Treatment for Other Conditions in the Study Eye**

416 An eye should not be enrolled that is anticipated to require intraocular treatment for another
417 condition during the study. If a condition develops during follow-up requiring prompt treatment,
418 it is at investigator discretion.

419 **4.2.3 Treatment in the Non-Study Eye**

420 Treatment in the non-study eye is at investigator discretion, except that gas injection for VMT is
421 not permitted in the non-study eye during the study.

422

CHAPTER 5: STUDY DEVICE

423

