654 The analysis plan synopsis in this chapter contains the framework of the anticipated final
655 analysis plan.

656 **8.2 Statistical Hypotheses**

657 A test of superiority will be used in evaluating the following hypotheses for the primary
658 outcome:

659 Null Hypothesis (H₀): There is no difference in the proportion of eyes with central VMT release
660 without rescue treatment between the PVL and observation groups at 24 weeks.

661 Alternative Hypothesis (H_a): There is a difference in the proportion of eyes with central VMT
662 release without rescue treatment between the PVL and observation groups at 24 weeks.

663 Similar hypothesis tests will be conducted for all secondary, exploratory, and safety outcomes.

664 **8.3 Sample Size**

665 **8.3.1 Outcome Projections:**

666 *Observation Group (sham injection)*

667 In a consecutive case series of 106 eyes with a median follow-up time of 18 months,⁶ the
668 proportion of eyes with spontaneous VMT release was 32%. The proportion of eyes with VMT
669 release at 6 months in the Sham Groups of the randomized controlled trials MIVI-TRUST¹⁰
670 (N = 188) and OASIS (N = 74),¹¹ which compared ocriplasmin versus sham for VMT, were
671 approximately 13% and 10%, respectively. Dugel et al.¹¹ also found that the proportion of eyes
672 with VMT release was greater among eyes that had MH at baseline. Macular hole was present at
673 baseline in approximately 36% of the OASIS Sham Group and 25% of the MIVI-TRUST Sham
674 Group.

675 *PVL group*

676 Three case series provide estimates of VMT release with C₃F₈ gas. A study of 15 eyes (1 with
677 MH) from Rodrigues et al.²³ showed release of VMT in 60% of eyes through 6 months. Steinle
678 et al.²⁴ showed 83% success among 30 eyes (3 with MH) through 62 days. Finally, Chan et al.²⁵
679 (2017) showed 86% success among 50 eyes (15 with MH) over 9 weeks. In addition, Chan et al.
680 reported higher rates of VMT release among eyes with MH. The release rate among eyes with
681 VMT only in Chan et al. was 80%.²⁵

682 **8.3.2 Sample Size Estimates**

683 Table 1 shows sample size estimates for the primary analysis under varying assumptions for the
684 proportion of eyes with VMT release within the 2 groups. These calculations assume a Type I
685 error rate of 5%, 90% power, and a two-sided test of superiority (See Section 8.6) with a null
686 hypothesis of no difference between the groups (Section 8.2).

687

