Table 1: Comparison of Proportion with VMT Release: Total Sample Size

Release in PVL Group	Release in Sham Group		
	10%	20%	30%
50%	52	104	248
60%	34	60	112
70%	24	38	62

688 For true outcome proportion of 60% (PVL) vs 30% (sham injection), a sample size of 112 (56
 689 per group) gives 90% power to reject the null hypothesis of no difference. Adjusting for possible
 690 loss to follow-up of 10% gives a final sample size of 124 (62 per group).

691 **8.4 Outcome Measures**

692 *For the outcomes below, rescue treatment includes vitrectomy, ocriplasmin, or additional
 693 pneumatic vitreolysis during the course of the study.*

694 Primary Efficacy Outcome:

- 695 • Proportion of eyes with central VMT release* without rescue treatment at 24 weeks.
 - 696 ○ For purposes of description only, the distribution of eyes within treatment group
 697 by the following categories at 24 weeks will be tabulated without statistical
 698 comparison:
 - 699 ▪ Central VMT release without rescue treatment
 - 700 ▪ Central VMT release with rescue treatment
 - 701 ▪ No central VMT release and no rescue treatment
 - 702 ▪ No central VMT release despite rescue treatment

703 Secondary Efficacy Outcomes:

- 704 • Proportion of eyes with central VMT release* without rescue treatment through 24 weeks
 705 (time-to-event analysis).
- 706 • Proportion of eyes with central VMT release and vitreopapillary traction release* without
 707 rescue treatment at 24 weeks.
- 708 • Mean change in visual acuity letter score from baseline at 24 weeks.
- 709 • Proportion of eyes with at least 10-letter gain (increase) in visual acuity from baseline at
 710 24 weeks.
- 711 • Proportion of eyes with at least 10-letter loss (decrease) in visual acuity from baseline at
 712 24 weeks.
- 713 • Proportion of eyes receiving rescue treatment before the 24-week visit.
 - 714 ○ For purposes of description only, the following will be tabulated within treatment
 715 group without statistical comparison:
 - 716 ▪ Proportion of eyes receiving rescue treatment before the 24-week visit or
 717 for which rescue treatment is planned at the 24-week visit and medical
 718 records confirm rescue treatment occurred within the subsequent 12
 719 weeks.

720 ■ Type of rescue treatment.

721 Exploratory Efficacy Outcomes:

722 • Mean change in shape discrimination hyperacuity from baseline at 24 weeks.

723 • Proportion of eyes with ellipsoid zone* integrity at 24 weeks.

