65 The data from the ITT cohort will be analyzed according to the group to which the participants
66 were assigned through randomization, regardless of treatment actually received.

67 A per-protocol analysis will be performed to provide additional information regarding the
68 magnitude of the treatment effect. The per-protocol analysis will only be performed if more than
69 10% of randomized participants would be excluded by these criteria (e.g., 13 or more
70 participants if exactly 124 are enrolled).

71 The ITT analysis is considered the primary analysis. If the results of the per-protocol and ITT
72 analyses give inconsistent results, then the per-protocol analysis will be interpreted with caution.
73 In this scenario, exploratory analyses will be performed to evaluate possible factors contributing
74 to the differences.

75 **1.4 Analysis of the Primary Efficacy Outcome**

76 The primary outcome of central VMT release without rescue treatment at 24 weeks is a binary
77 variable that is graded by the central reading center. Logistic regression will be used to test the
78 hypothesis of superiority. The risk difference for the treatment group effect (estimated with
79 conditional standardization)⁴, along with the 95% confidence interval (estimated with the delta
80 method)⁴ and *P* value will be used to compare treatment groups. To aid in interpretation of the
81 risk difference, observed outcome proportions will be reported for each treatment group.

82 Since the chance of re-attachment after release before 24 weeks is highly unlikely, an eye with
83 central VMT release without rescue treatment prior to 24 weeks will be considered to have met
84 the outcome through 24 weeks if the participant is lost to follow-up. Similarly, any eye receiving
85 rescue treatment prior to 24 weeks will be considered not to have met the outcome through 24
86 weeks.

87 Multiple imputation will be used to impute missing data for eyes lost to follow-up that did not
88 have prior release or rescue treatment documented. The imputation model will treatment group,
89 and VMT status at 1, 4, 12, and 24 weeks.

90 A sensitivity analysis will be conducted using the same approach as above, but without multiple
91 imputation (i.e., complete-case analysis).

92 **1.5 Analysis of the Secondary and Exploratory Efficacy Outcomes**

93 The ITT analysis cohort will be used for all secondary and exploratory outcomes.

94 **1.5.1 Secondary Efficacy Outcomes**

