95 Development of central VMT release without rescue treatment through 24 weeks is a time-to-
96 event outcome graded by the central reading center that will be modeled with Cox proportional
97 hazards regression and robust variance estimation. The hazard ratio along with the 95%
98 confidence interval and *P* value will be used to compare treatment groups. To aid in
99 interpretation, a Kaplan-Meier plot will be constructed and the cumulative probability of the
100 outcome will be estimated at the final time point for each group. Data from eyes not observed to
101 have release or that receive rescue treatment will be censored on the date of their final visit (not
102 the date of rescue treatment).

103 Change in visual acuity letter score from baseline to 24 weeks is a continuous variable that will
104 be analyzed using a general linear model with robust variance estimation. Baseline visual acuity
105 will be included as a covariate. The adjusted treatment group difference, 95% confidence
106 interval, and *P* value will be presented. To aid in interpretation, least squares means and
107 associated 95% confidence intervals will be reported for each treatment group. Missing data will
108 be imputed with multiple imputation. The imputation model will include treatment group,
109 baseline visual acuity, visual acuity at 1, 4, 12, and 24 weeks, and VMT status at 1, 4, 12, and 24
110 weeks.

111 The proportions of eyes with at least 10-letter gain (increase) and at least 10-letter loss (decrease)
112 in visual acuity from baseline are binary variables that will be analyzed with logistic regression
113 utilizing the imputed data sets from the analysis of mean change in visual acuity from baseline.
114 Baseline visual acuity will be included as a covariate.

115 The proportion of eyes receiving rescue treatment before the 24-week visit is a binary variable
116 that will be analyzed with logistic regression. Complete-case analysis (no imputation of missing
117 data) will be used for this outcome.

118 **1.5.2 Exploratory Efficacy Outcomes**

119 Change in SDH is a continuous variable that will be analyzed similarly to change in visual acuity
120 but substituting baseline and follow-up SDH for visual acuity. Complete-case analysis (no
121 imputation of missing data) will be used for this outcome. Shape discrimination hyperacuity
122 ranges from -1 to +1. On the myVisionTrack test being used in this study, normal SDH is -0.60
123 or less.

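### In the time-to-event analysis, a rescued eye that leaves the study early is censored at its last visit, although SAP 1.4 makes it a known failure; if this happens, Kaplan-Meier release can be overstated in its arm

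*SAP*

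**What the plan says.** The primary outcome and the first secondary outcome share one event: central VMT release without rescue. The two analyses treat a rescued eye differently.

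- **Primary analysis (SAP 1.4).** Any eye given "rescue treatment prior to 24 weeks will be considered not to have met the outcome through 24" weeks. Multiple imputation is limited to lost eyes with neither release nor rescue on record. A rescued eye that leaves is therefore a known failure and is not missing.
- **Time-to-event analysis (SAP 1.5.1).** Eyes not observed to "have release or that receive rescue treatment will be censored on the date of their final visit". A parenthesis adds that the rescue date is not to be used. The model is Cox regression, and the Kaplan-Meier cumulative probability at the final time point is reported for each group.
- **Protocol 8.7.1** has the same final-visit rule, without the parenthesis.

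Neither SAP 1.5.1 nor SAP 1.14 (Missing Data) carries a rescued eye forward once it has left.

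**The concern.** Kaplan-Meier and Cox assume that a censored eye has the same later chance of the event as comparable eyes still under follow-up. An eye rescued before release has no such chance, because release without rescue is no longer possible for it. Censoring it at its last visit passes its weight to eyes that can still release, and this raises the estimated release probability.

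The parenthesis in SAP 1.5.1 shows that the authors saw the problem: rescued eyes are not to be censored at rescue. The rule achieves this only for rescued eyes that stay to 24 weeks.

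At stake is a Kaplan-Meier release figure that could differ from the primary proportion, for the same event and the same eyes, because of how one date is derived. SAP 1.17 reports a smaller final sample than planned, so each such eye would weigh more.

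**Working it through.** **Inputs from the plan.** Protocol 8.3.2 plans on "error rate of 5%, 90% power, and a two-sided test of superiority", with 60% release on PVL and 30% on sham. Pooled-variance formula, per group: [1.960·√(2·0.45·0.55) + 1.282·√(0.6·0.4 + 0.3·0.7)]² / 0.3² = 55.7, so 56 per group and 112 in total. This reproduces the plan. The plan then states that "loss to follow-up of 10% gives a final sample size of 124 (62 per group"; 112/0.9 = 124.4, which agrees to rounding. Visits follow the protocol: "Follow-up will occur at 1, 4, 12 and 24 weeks".

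**Inputs assumed.** The documents give no count of rescued eyes that left, no release times and no final sample size. I use the planned 62 per arm and illustrative releases at weeks 1/4/12/24 of 7/11/11/8 in PVL (37/62 = 59.7%) and 2/6/6/5 in sham (19/62 = 30.6%).

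**Small worked example.** Take 20 eyes in one arm: 8 release at week 4, 2 are rescued and last seen at week 6, 3 release at week 12, 1 releases at week 24, and 6 never release.

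- Primary rule: 12/20 = 60.0%.
- Kaplan-Meier as written: 1 − (12/20)(7/10)(6/7) = 64.0%.
- Kaplan-Meier with the rescued eyes kept at risk: 1 − (12/20)(9/12)(8/9) = 60.0%.

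**General form.** Let N be the arm size, R the unreleased eyes just before the rescued eyes leave, L the number of rescued eyes that leave at that point, and D the later releases in the arm. With no other censoring:

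- as written: release = 1 − (R/N)·(R − L − D)/(R − L)
- with rescued eyes kept: release = 1 − (R − D)/N
- difference = D·L / [N·(R − L)]

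The difference is never negative, and it is zero if L = 0 or D = 0. In the 20-eye example it is 4·2/(20·10) = 4.0 points.

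**At 62 per arm.** For one rescued PVL eye last seen at week 4, R = 62 − 7 − 11 = 44 and D = 11 + 8 = 19, so the difference is 19/(62·43) = 0.71 points. For one sham eye, R = 54 and D = 11, so it is 11/(62·53) = 0.33 points. Overstatement in percentage points:

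| Arm | Rescued eyes that leave | Last visit week 1 | Week 4 | Week 12 |
|---|---|---|---|---|
| PVL | 1 | 0.90 | 0.71 | 0.40 |
| PVL | 3 | 2.79 | 2.24 | 1.29 |
| PVL | 6 | 5.92 | 4.84 | 2.87 |
| Sham | 1 | 0.46 | 0.33 | 0.17 |
| Sham | 3 | 1.44 | 1.04 | 0.54 |
| Sham | 6 | 3.05 | 2.22 | 1.15 |

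Six eyes is about 10% of an arm. It is an upper case in which the whole planned loss consists of rescued eyes.

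**Hazard ratio.** Cox model with Efron ties on the same data, last visit at week 4. With no rescued leavers, or with them kept at risk, HR = 2.48 (95% CI 1.42 to 4.31, model-based variance).

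| Rescued leavers, PVL / sham | HR as written |
|---|---|
| 3 / 3 | 2.52 |
| 3 / 0 | 2.61 |
| 0 / 3 | 2.39 |
| 0 / 6 | 2.30 |

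**Check on the remedy.** The 24-week target is day 168, but the analysis window in SAP 1.13 runs to day 280. Suppose rescued eyes were kept only to day 168. In the 20-eye example, put all 24-week visits on day 175 and let both rescued eyes stay. The rule as written gives 60.0%. A day-168 cut-off gives 1 − (12/20)(9/12)(6/7) = 61.4%, a bias where none existed. The end point must therefore not fall before the last 24-week analysis visit.

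**The case against.** **Rescued eyes are expected to stay.** Scheduled visits apply to both groups whatever treatment follows. Vitrectomy under Protocol 4.2.1 counts as per-protocol. Two of the four descriptive outcome categories at 24 weeks are for rescued eyes, and the Coordinating Center helps track participants whom a site cannot contact. Nothing in the documents links rescue to exit. This stands, and it makes the point conditional. It does not supply a rule for the eye that does leave.

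**Final visit could mean the 24-week visit, as in SAP 1.0.** This does not stand. The same sentence covers unreleased eyes lost to follow-up, which have no 24-week visit, so it must mean the last visit attended.

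**The two analyses were never meant to agree exactly.** The primary analysis imputes unrescued lost eyes, while Kaplan-Meier censors them. This is true, but it concerns eyes whose status is unknown. The status of a rescued eye is known.

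**Stronger readings that the documents do not support.**

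- A reader might infer that reported release is overstated in any event, or that all rescued eyes are mishandled. Rescued eyes that complete 24 weeks are handled correctly, and no document shows that any rescued eye left.
- A reader might infer that the treatment effect is biased in favour of PVL. The hazard ratio moves either way, depending on which arm loses rescued eyes, and the shifts shown are small against its confidence interval.
- A reader might infer that the final-visit date is also wrong for unrescued eyes, because a last visit may lack a gradable OCT: "Testing procedures at unscheduled visits are at investigator discretion". However, Protocol 4.1.1 requires OCT at every scheduled visit and provides for repeating an ungradable scan. Any remaining effect would enlarge the risk set and lower estimated release, and nothing in the documents allows it to be sized. I do not raise it.

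**Conclusion.** The point holds as a conditional, minor defect in one secondary analysis. SAP 1.5.1 and Protocol 8.7.1 censor an eye rescued before release at its last attended visit, while SAP 1.4 already knows its outcome. If such an eye leaves before later releases in its arm, Kaplan-Meier release for that arm is too high.

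The sizes rest on assumed release times, assumed numbers of rescued leavers and the planned 62 per arm. On those assumptions, one such eye adds 0.4 to 0.9 points in PVL or 0.2 to 0.5 in sham. A smaller final sample would raise the weight of each eye. The primary analysis is untouched.

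**What to change.** Replace the censoring sentence in SAP 1.5.1 with:

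*Eyes that receive rescue treatment before release remain in the risk set without an event through the final time point at which the Kaplan-Meier probability is reported (not before the last 24-week analysis visit in the study), whether or not they leave the study; unrescued eyes without release are censored at their final visit.*

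For the release figure, an equivalent is to treat rescue as a competing event and report cumulative incidence.

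Make the same change in Protocol 8.7.1, so that the two documents do not diverge. SAP version 2.0 was itself written after study data had been reviewed, so list this change in SAP 1.17 as also made after data review.

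The cost is one sentence in each document, one entry in the revision list and one derived date. No new data are needed. The Kaplan-Meier release figure may fall slightly, or stay the same if no rescued eye left early.

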158 calculated. The proportion of participants experiencing each outcome will be compared with
159 Barnard's unconditional exact test. The following systemic adverse events are of primary
160 interest:

161 • Death
162 • Serious adverse event (at least one)

163 The following systemic adverse events are of secondary interest and will be tabulated without
164 statistical comparison:

165 • For each MedDRA System Organ Class, proportion of participants with at least one
166 serious event

167 **1.7 Intervention Adherence**

168 Adherence will be defined as completion of the treatment assigned at randomization: either PVL
169 or sham injection.

170 **1.8 Protocol Adherence and Retention**

171 Protocol deviations and visit completion rates (excluding deaths) will be tabulated for each
172 treatment group.

173 **1.9 Baseline Descriptive Statistics**

174 Baseline characteristics will be tabulated by treatment group and summary statistics appropriate
175 to the distribution will be reported.

176 **1.10 Planned Interim Analyses**

177 There is no formal interim analysis planned for this study. The Data and Safety Monitory
178 Committee (DSMC) will review safety and outcome data approximately every 6 months while
179 the study is ongoing.

180 **1.11 Subgroup Analyses**

181 Subgroup analyses, i.e., assessments of effect modification (interaction), will be conducted for
182 the primary outcome. These analyses will be considered exploratory. Additionally, interpretation
183 of the analyses will depend on whether the primary analysis demonstrates a significant treatment

184 group difference; in the absence of such a difference, subgroup analyses will be interpreted with
185 caution.

186 The general approach for these exploratory analyses will be to add an interaction term for the
187 subgroup factor by treatment into the primary analysis model. In addition, within-subgroup risk
188 differences and 95% confidence intervals will be estimated from the interaction model if the
189 interaction P value is less than .05. Subgroup analyses will use data from eyes that complete the
190 24-week visit or have VMT release or rescue treatment prior to 24 weeks (i.e., complete case
191 analysis as described in section 1.4).

192 The primary subgroup analysis will evaluate the effect of ERM presence within 1 mm of the
193 center of the macula at baseline. In previous studies, eyes with ERM had lower release rates
194 compared with eyes not having ERM.¹⁻³

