195 Secondary subgroup analyses will include ERM presence at the site of vitreous adhesion, lens
196 status (phakic or pseudophakic), retinoschisis, subretinal fluid within the central 1 mm, length of
197 adhesion on OCT (less than or equal to 1500 microns or greater than 1500 microns), and diabetes
198 status (has diabetes or does not have diabetes). Subgroups will be defined by the value at
199 baseline.

200 There are no data to suggest that the treatment effect will vary by sex or race/ethnicity. However,
201 both of these factors will be evaluated in exploratory subgroup analyses as mandated by National
202 Institutes of Health (NIH) guidelines.

203 Subgroup factors will be analyzed as categorical and continuous or ordinal variables where
204 possible. Secondary and exploratory subgroup analyses will only be conducted if there are at
205 least 20 eyes in each subgroup for each treatment group. The primary subgroup analysis will be
206 conducted regardless of sample size.

207 **1.12 Multiple Testing**

208 There will be no formal adjustment for multiple testing. Only $P \leq .05$ will be considered of
209 interest.

210 **1.13 Visit Windows for Analysis**

211 The analysis windows for visits will be defined according to Table 1. If multiple visits fall within
212 the same window, priority will be given to the protocol visit over unspecified visits. If there is no
213 protocol visit in the window, then the visit closest to the target date (but within the analysis
214 window) will be designated as the analysis visit. Visit windows will be filled in the following
215 order to handle visits occurring on the border of two windows: 24 weeks, 12 weeks, 4 weeks, 1
216 week.

217 **Table 1. Analysis Windows**

Visit \pm Protocol Window	Target	Analysis Window
1 week (-4 days to +3 days)	7 days	1 day – 2 weeks (1 – 14 days)
4 (± 1) weeks	28 days	2 – 8 weeks (14 – 56 days)
12 (± 2) weeks	84 days	8 – 18 weeks (56 – 126 days)
24 (± 4) weeks	168 days	18 – 40 weeks (126 – 280 days)

218 **1.14 Missing Data**

219 The strategy for handling missing data generally is included with the description of each
220 analysis. For analyses using multiple imputation, the Markov chain Monte Carlo (MCMC)
221 method with 100 imputations will be used. Where otherwise not specified, only participants with
222 non-missing data are included in analyses (i.e., complete-case analysis).

223 **1.15 Outliers**

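### Does dropping only the unresolved lost eyes spoil the complete-case sensitivity and subgroup analyses?

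*SAP*

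**What the plan says.** SAP 1.4 (and Protocol 8.6) sets three rules for the primary outcome.

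- An eye that released and was then lost is a success: "Since the chance of re-attachment after release before 24 weeks is highly unlikely, an eye with" "central VMT release without rescue treatment prior to 24 weeks will be considered to have met" the outcome.
- A rescued eye is a failure, lost or not: "rescue treatment prior to 24 weeks will be considered not to have met the outcome through 24" weeks.
- Only the remaining lost eyes are imputed: "Multiple imputation will be used to impute missing data for eyes lost to follow-up that did not" have either event on record.

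The sensitivity analysis then switches imputation off: "A sensitivity analysis will be conducted using the same approach as above, but without multiple" imputation. SAP 1.11 and Protocol 8.13 use the same set for subgroups and name its members, namely eyes with the "24-week visit or have VMT release or rescue treatment prior to 24 weeks (i.e., complete case" analysis as in 1.4). Subgroup analyses are declared exploratory. Within-subgroup estimates are conditional: "differences and 95% confidence intervals will be estimated from the interaction model if the" interaction P value is below .05. Secondary and exploratory subgroups need at least 20 eyes per subgroup in each arm. The ERM subgroup is analysed whatever the numbers.

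**The concern.** With imputation off, the only eyes removed are lost eyes with no release and no rescue. Keeping a lost eye therefore depends on its outcome. When rescue is rare, the eyes removed are mostly future failures, and both arms look better than they are even if loss is pure chance.

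The sensitivity analysis is there to show whether imputation drives the primary result. If its own set is distorted, part of any gap between the two analyses comes from the inclusion rule and says nothing about imputation. A reader who takes complete case to mean completers would not expect that. The same set carries the ERM subgroup, in a trial that ended smaller than planned.

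**Working it through.** **Inputs.** Protocol 8.3.2: 60% against 30%, 56 evaluable eyes per arm, 10% loss, 62 per arm. Protocol 1.1.3: gas release 40% at one month and 60% by 6 months. Protocol 1.1.2 and 8.3.1: control release 10% at 28 days and about 13% at 6 months in one trial programme, 6% and about 10% in another. Rescue rates, loss timing, loss by arm and the final sample size are not given, so values for these are assumptions.

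**The plan's own figure.** With pooled variance and no continuity correction, n = [1.960 x sqrt(2 x 0.45 x 0.55) + 1.282 x sqrt(0.24 + 0.21)]^2 / 0.30^2 = 55.7, so 56 per arm and 112 in total. 112/0.9 = 124.4; the protocol states 124.

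**Expected arm rate under the rule.** Let p be the true success rate, L the random loss, and q and r the fractions of lost eyes released and rescued before loss:

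kept rate = [(1-L)p + Lq] / [(1-L) + L(q+r)].

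It equals p only if q/(q+r) = p, or if no eye has an event before loss.

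**Design case, L = 10%, r = 0.** Setting q to early release assumes that every lost eye left after month 1 and before any later release.

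- Gas, q = 40%: (0.54 + 0.04)/(0.90 + 0.04) = 61.7%.
- Sham, q = 30% x 10/13 = 23.1%: (0.27 + 0.0231)/(0.90 + 0.0231) = 31.7% (31.75%).
- Difference: 29.95 points, a shift of -0.05.

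**Other cases.**

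| Case | Gas | Sham | Shift in difference |
|---|---|---|---|
| Sham 13%, q = 10% | 61.7% | 14.0% | +0.75 |
| Sham 10%, q = 6% | 61.7% | 10.6% | +1.1 |
| 80/30, two-thirds early (assumed) | 81.1% | 31.5% | -0.4 |
| 60/30, q = 60%/10% (assumed) | 62.5% | 30.8% | +1.7 |
| Design case, loss 15%/5% (assumed) | 62.6% | 30.8% | +1.8 |
| Design case, loss 5%/15% (assumed) | 60.8% | 32.7% | -1.9 |
| q = 60%/10%, loss 15%/5% (assumed) | 63.8% | 30.4% | +3.5 |

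If 10% of lost eyes in both arms had been rescued, the design-case shift is -0.4. At 20% loss with two-thirds of releases early in both arms, the arms read 0.56/0.88 = 63.6% and 0.28/0.84 = 33.3%, a difference of 30.3.

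**Scale.** The standard error of the difference is sqrt(0.45/56) = 9.0 points, and 10.6 at an assumed 40 per arm.

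**Simulation.** A visit-level run (2 million eyes per arm, 10% random loss, no rescue, similar timing) gave 61.8% and 31.5%, difference 30.3. With late sham release the difference was 31.1.

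**The tested scale.** Both analyses use logistic regression. With r = 0 and q = fp, the rule multiplies each arm's odds by (1-L+Lf)/(1-L). At L = 10% and f = 2/3 this is 0.9667/0.9 = 1.074 in every cell, so the odds ratio stays at 3.50. Take an assumed ERM interaction, gas 80% without ERM and 40% with, sham equal. The gas rates become 81.1% and 41.7%. The interaction odds ratio is 6.0 before and after, while the contrast in points goes from 40.0 to 39.4.

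**A check already in the plan.** SAP 1.5.1 censors eyes without release at their final visit. In the gas design case, of 100 eyes, 60 are unreleased at month 1; 6 are then censored, and 18 of the remaining 54 release. Kaplan-Meier gives 1 - 0.60 x 36/54 = 60%, the true rate, with no imputation.

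**Would completers only be better?** It is unbiased under random loss. Under three assumed non-random patterns, same in both arms at the design rates:

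| Loss pattern | Gas bias, completers / plan | Shift in difference, completers / plan |
|---|---|---|
| Early-released lost 15%, others 5% | -1.8 / +0.8 | -0.02 / -0.02 |
| Early-released lost 5%, others 15% | +1.8 / +2.6 | -0.05 / -0.10 |
| 10% rescued; rescued lost 30%, others 8% | +1.5 / +0.8 | +0.7 / -0.3 |

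**The case for a change.** The strongest case for acting is that the bias needs no unusual missingness: it appears under completely random loss, in the one analysis that SAP 1.4 sets beside the imputed result. Arm proportions are reported, and they move by 0.6 to 2.5 points in the equal-loss, no-rescue cases at 10% loss. Since SAP 1.17 the effect is reported as a risk difference, which does not share the invariance of the odds ratio. That invariance also fails once loss, timing or rescue differs between arms, and 15% against 5% loss can move the difference by 2 to 3.5 points.

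All of that stands as description. So does a further limit: if the logistic model fails to converge, SAP 1.16 turns imputation off in the primary analysis too. With treatment as the only term, that essentially needs an arm at 0% or 100%. The other arm keeps its bias, for example +1.7 points for gas at 60% against sham at 0%. The Kaplan-Meier estimate does not cover subgroups, and lost rescued eyes complicate it.

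What does not stand is the step to a change. SAP 1.11 lists the members of the set, so only the statistical implication is left unsaid. Restricting to completers throws away known outcomes of randomised eyes (about 6.2 x 0.40 = 2.5 gas and 6.2 x 0.231 = 1.4 sham eyes of 62 per arm), and the table above shows no consistent gain. Imputing with subgroup terms runs against SAP 1.17, which removed ERM from every imputation model because of the small sample. A two-level secondary subgroup already needs 4 x 20 = 80 eyes before it is run.

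**Conclusion.** The observation is correct, and the plan can stay as it is. At 10% random loss with little rescue, the rule overstates arm release rates by roughly 1 to 2.5 points. With similar loss in both arms and the documents' timing, it moves the difference by about 1 point or less, against a standard error of 9.0 or more. With equal loss and timing and no rescue, the odds ratio and the interaction are unchanged. The imputed primary analysis is affected only through the SAP 1.16 fallback.

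The rule is a fair trade-off. It keeps outcomes that are known, it was in Protocol 8.6 and 8.13 before the post-data revision, and no alternative set is shown to be better. An analyst can read the sensitivity result beside the Kaplan-Meier probability in SAP 1.5.1. A note that the set is selected on early outcome would help a reader but would alter no result.

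The sizes rest on assumed loss timing and rescue, and on timing shares borrowed from a 15-eye gas series and from control arms that included macular holes, which this trial excludes. Loss that differs strongly between arms would make the shift larger.
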